^a 1 cycle = 28 days. Cycles repeat on a continuous basis with no interval between cycles.

^b Weekly visit may be omitted if Visit Y is within 2 days of weekly visit.

• Visit Y is only utilised if the dosing schedule is intermittent. Visit Y represents the last AZD7648 dosing day in the first block of AZD7648 treatment in a cycle eg, CCI

^d There are no visit windows in Cycle 0 and Cycle 1.

- e With the patient's consent, as part of the medical history, any available information on known tumour gene mutations will be collected.
- f Targeted physical examinations only required if clinically indicated (indication should be stated).
- ^g Vital signs then ECG measurements will be collected prior to PK blood draws at all PK sample timepoints. Timepoints may be modified based on the initial data obtained.
- ^h Serious adverse events (SAEs) only to be collected between AZD7648 discontinuation and disease progression.
- ⁱ Women of child-bearing potential must have a negative urine or serum pregnancy test at screening, a confirmatory test before treatment on Day 1 (Cycle 0 or Cycle 1), at regular intervals during treatment and at AZD7648 discontinuation. If results are positive, the patient is ineligible/must be discontinued from the study treatment and not discontinued from the study. The patient will continue to be followed up according to the study protocol.
- ^j TSH to be measured at baseline and every 3 cycles. CRP to be collected at baseline, then on Day 1 from Cycle 1. Urinalysis at Cycle 0, Cycle 0 + 1 and Day 1 of each cycle. Tumour markers (if relevant) to be measured at baseline and on Day 1 of every cycle from Cycle 1 (only if elevated at baseline).
- k LVEF assessment (ECHO or MUltiGated Angiography [MUGA]) and review must occur at screening and prior to dosing at Cycle 4 Day 1 and Cycle 7 Day 1 (-7 day window).
- ¹ Provision of archival tumour samples are mandatory for all patients. The samples may be submitted retrospectively.
- ^m Fresh biopsy samples are encouraged in Part A (particularly in patients with accessible tumours) and are mandatory for patients enrolled into Part A optional PD expansion cohorts (or a PD subgroup of an optional efficacy expansion cohort). Serial biopsies will be collected during screening, on treatment (any time in Cycle 1 between Days 3 and Visit Y 2 to 8 hours [h] post AZD7648 dosing), and on progression.

		-	-	 	
n	CCI				
0	I CCI				

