14.1.2 Dose escalation scheme

For Combination Module 1, the dose escalation schedule is presented in Figure 9. When there is more than one patient enrolled to a dose cohort, sentinel dosing will be applied with a single patient exposed for a minimum of 48 hours after Cycle 1, Day 1 before further patients are enrolled at that dose level. In the absence of any significant toxicities in the first patient, the patients for the remainder of the cohort may be enrolled, concurrently or sequentially, based upon the decision of the SRC.

For each cohort in dose escalation a SRC will review the safety of the first and each subsequent cohort.

Figure 9AZD7648 combinations study flow chart

RP2D=recommended Phase II dose

The starting dose of PLD is 40 mg/m², administered by IV infusion once every 4 weeks, for a maximum of 6 cycles (Table 15). Patients who are deriving clinical benefit may continue AZD7648 beyond 6 cycles as monotherapy in the continuation phase; using a dose and schedule declared tolerated in the Core Module.

During Part A (dose escalation), a single dose of AZD7648 will be administered to enable collection of blood samples for PK analyses, followed by a drug washout of CCI (Figure 10). The dose of PLD may also be escalated to 50 mg/m² (or de-escalated to 30 mg/m²) every 4 weeks with agreement of the SRC. Intermittent schedules for AZD7648 will also be explored.
Cohort	PLD dose (mg/m ²)	AZD7648 dose CC (mg)	No. days of AZD7648 in each cycle
-1	30	CCI	E
Starting Cohort 1	40	CCI	T
2	40	CCI	•
3	40	CCI	e.
4	40	CCI	CC .
Cohort n	40	Escalate to monotherapy MTD or MFD in no more than 50% increments	
Maximum dose level	50	CCI	CCI

Table 15 Illustrative AZD7648 dose escalation schedule

CCI=**CCI**; MFD=maximum feasible dose; MTD=maximum tolerated dose; PLD=pegylated liposomal doxorubicin.

Actual doses and schedules may vary using Bayesian adaptive design modelling based on emerging safety and tolerability data, and subject to Safety Review Committee (SRC) agreement. The dose of PLD may also be escalated to 50 mg/m^2 (or de-escalated to 30 mg/m^2) administered once every 4 weeks.

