The reference date for all assessments except for tumour assessments, will be the start of the study treatment in cycle 0 (i.e., cycle 0, day 1). There is no study day 0 for this study. Date of cycle 1, day 1 dosing will be considered as the start date for the calculation of efficacy endpoints (tumour response, PFS), which follows CSP visit window starting from cycle 1, day 1. The study day will be displayed in the data listings. If an event starts before the reference start date, the study day displayed on the listing will be negative.

Time Windows

Time windows will need defining for any presentations that summarise values by visit.

Given the washout period between Cycle 0 and Cycle 1 can vary between patients (3-7 days per CSP) and therefore study day of Cycle 1 Day 1 onwards will vary, for the purposes of windowing assessments the study day of visits from Cycle 1 Day 1 onwards will be adjusted in order to allow the same window to be applied across patients. This will not impact on study day displayed in listings and will be used only by programming as an intermediate step to assign analysis visits. The amount to adjust the study day by will be derived assuming the planned day for Cycle 1 Day 1 is day 8 for all patients:

Adjustment (days) = 8 – actual Cycle 1 Day 1 study day

Study day for all safety assessments from Cycle 1 Day 1 onwards will be adjusted by this amount when assigning assessments to analysis visits. Actual, unadjusted study day will be presented in listings.

The following conventions should apply:

- Inclusion within the time window should be based on the actual date and not the intended date of the visit.
- The visit window following baseline will be constructed as per [Table 4](#) for the safety assessments
- For summaries showing the maximum or minimum values, the maximum/minimum value recorded on treatment will be used (regardless of where it falls in an interval).
- Listings should display all values contributing to a time point for a patient.
- Often the most meaningful summaries focus on extreme values rather than summaries at each visit but if summaries over time are felt to be required:
- For visit based summaries

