C2	Day 15	Cycle 1 Day 15	C2D1 + 11 day to C2D1 + 17 days
Cx (≥3)	Day 1	Day1 of any cycle ≥ 3	
From:
 
Monotherapy: Cx-1D1 + 28 – 2 days
 
or
 
first day of intake of AZD7648 after Cx-1D1+28) – 2 days; if AZD7648 is off on Cx-1D1+28-1 day.
 
Combinations: (Day 1 of associated anticancer agent for Cx or Cx-1D1 + 28) -2 days; if associated anticancer agent stopped
 
or

			
(first day of intake of associated anticancer agent after Cx-1D1+28) – 2 days; if associated anticancer agent is off on Cx-1D1+28-1.
 
To:
 
Monotherapy: Cx-1D1 + 28 + 2 days
 
or
 
first day of intake of AZD7648 +1 day after C1D1+28; if AZD7648 is off on C1D1+28-1 day.
 
Combinations: (Day 1 of associated anticancer agent for Cx or Cx-1D1 + 28) +2 days; if associated anticancer agent stopped.
 
or
 
(first day of intake of associated anticancer agent after Cx-1D1+28) +2 days; associated anticancer agent is off on Cx-1D1+28-1 day.

-	-	IP Disc ^[b]	IP Disc + 1 day
		28 day safety follow-up after IP Disc	
IP Disc +28 -7 days
 
To
 
ID Disc + 28 +7 days

^[a] Previous interval is C1D1.

^[b] Investigational product discontinuation.

Visit windowing for radiological tumour evaluations

The radiological tumour assessments done within 28 days prior and up to pre-dose on cycle 0 day 1 will be considered as baseline. In case of multiple evaluations in the above time period, the value closest to cycle 0, day 1 will be taken as baseline.

A windowing rule will be applied and will follow the protocol allowed visit window; therefore, any RECIST scan performed within ± 1 week of the protocol scheduled visit will be used for that visit. Given

scans will be done relative to Cycle 1 Day 1, the adjustments described for safety assessments will be done when windowing target lesion data.

Handling Missing data

No missing data will be imputed with the exception of the imputation rules described below.

Imputation for partial dates of adverse events, concomitant medication and death

Start and stop dates are collected on the CRF and measures will be taken to minimize missing in data collection. In case of partial information in these dates, the following rules will be used to impute the dates.

If start date is partial:

- Missing day - impute the 1st of the month unless month is same as month of first dose of study drug then impute first dose date.

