3.2.1.12 Echocardiogram

left ventricular ejection fraction (LVEF) is collected for all patients in combination module 1. Change of LVEF from baseline will be calculated at each scheduled post-baseline assessment time and summarised by part, by cohort and visit..

The absolute change from baseline will also be summarised by following categories:

- Any increase
- No change
- Any decrease
- 0 to <10% decrease
- 10 to <20% decrease
- $\geq 20\%$ decrease
- $\geq 10\%$ decrease and \geq Lower Limit Normal (LLN)

- $\geq 10\%$ decrease and $< LLN$
- $\geq 20\%$ decrease and $\geq LLN$
- $\geq 20\%$ decrease and $< LLN$

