4 ANALYSIS METHODS

4.1 General principles

The below mentioned general principles will be followed throughout the study:

- The planned arm and the actual arm for each patient will be assessed by study medical monitor and provided in a separate MS Excel sheet, which will be used for study summaries. This Excel file will be filed in the TMF at the end of the study.
- Unscheduled assessments will not be included in aggregate summaries and will be listed only. The assessments which are not included in the aggregate summary will be flagged in the listing. Unscheduled assessments will be included in the patient level figures.
- Descriptive statistics will be used for all variables, as appropriate. Continuous variables will be summarised by the number of observations, mean, standard deviation, median, upper and lower quartiles (as applicable), minimum, and maximum. For log transformed data it is more appropriate to present geometric mean, coefficient of variation (CV), median, minimum and maximum. Categorical variables will be summarised by frequency counts and percentages for each category.
- Descriptive statistics will only be presented if $n \geq 3$. If no patients have data at a given time point, then only $n = 0$ will be presented. If data are available for less than 3 participants, no summary statistics other than minimum, maximum and number of observations will be presented
- Unless otherwise stated, percentages will be calculated out of the analysis set total and for modules (core, combination 1 module)/ parts (Part A: dose escalation, Part B: expansion cohorts)/doses.
- For continuous data the mean and median will be rounded to 1 additional decimal place compared to the original data. The standard deviation will be rounded to 2 additional decimal places compared to the original data. Minimum and maximum will be displayed with the same accuracy as the original data.
- For categorical data, percentages will be rounded to 1 decimal place.

- SAS® version 9.4 or higher will be used for all analyses.
- It is acceptable to present large numerical values in more appropriate units. For example, an AUC value of 123,000 ng·h/mL may be reported as 123 µg·h/mL instead of 123,000 ng·h/mL. It is, however, important to keep the units consistent within the report and the precision consistent with that prior to conversion.

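### SAP Table 4 has no LVEF exception, so protocol-compliant tests on days -7 to -3 before Cycle 4 Day 1 and Cycle 7 Day 1 get no analysis visit

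*SAP*

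**What the plan says.** - **Protocol 10.1, Table 13 Part A, footnote k.** LVEF (echocardiogram or MUGA) must be measured and reviewed at screening and "prior to dosing at Cycle 4 Day 1 and Cycle 7 Day 1 (-7 day window"). These are the only two scheduled post-baseline LVEF tests. The general visit window in the same table for Day 1 of Cycle 3 onwards is ±2 days.
- **SAP 3.1, Table 4 (safety analysis).** For Day 1 of any cycle from 3 on, the lower limit in the combination module is "Combinations: (Day 1 of associated anticancer agent for Cx or Cx-1D1 + 28) -2 days; if associated anticancer agent stopped". The upper limit has the same form with +2 days. Table 4 has no LVEF row.
- **SAP 3.1, Time Windows.** "Inclusion within the time window should be based on the actual date and not the intended date of the visit". If several values lie within one window, the value closest to the scheduled date is used.
- **SAP 3.2.1.12.** "Change of LVEF from baseline will be calculated at each scheduled post-baseline assessment time and summarised by part, by cohort and visit". It adds: "The absolute change from baseline will also be summarised by following categories". It does not say whether those categories are counted by visit or on the worst value.
- **SAP 4.1.** "Unscheduled assessments will not be included in aggregate summaries and will be listed only". On small numbers: "If data are available for less than 3 participants, no summary statistics other than minimum, maximum and number of observations will be presented".
- **Protocol 14.1.2.** PLD is given for at most 6 cycles. "Patients who are deriving clinical benefit may continue AZD7648 beyond 6 cycles as monotherapy in the continuation phase".

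**The concern.** Echocardiogram is one of the variables under the primary safety objective, and it is collected only in this module. The protocol gives LVEF a wider window than other Day 1 assessments. Because the result has to be reviewed before dosing, booking the test several days ahead is a natural way to comply (my inference). The SAP took over the general ±2 day window but not the LVEF exception. In the same section, the rule for RECIST scans does follow the window that the protocol allows, so this looks like an omission rather than a choice.

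If Table 4 is programmed as written, the number of patients in the by-visit LVEF table depends on when each test was booked. Part A cohorts enrol 3 to 6 patients. If exactly 3 patients in a cohort are tested at a visit and one of them is tested early but within the protocol, n falls from 3 to 2. The SAP then shows only n, minimum and maximum for that cell.

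**Working it through.** There is no plan figure to reproduce. The check lays the two windows on one day scale, with day 0 as the actual Day 1 of the cycle.

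**Does Table 4 govern LVEF?** SAP Table 3 lists echocardiogram under safety data, and SAP 3.1 says that Table 4 sets the windows for safety assessments. So it does.

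**Cycle 4 Day 1, dosing on time**
- Allowed by footnote k: days -7 to 0, which is 8 days.
- Covered by Table 4 within that range: days -2, -1 and 0, which is 3 days.
- Not covered: days -7 to -3, which is 8 - 3 = 5 days.

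**Does another row catch those days?** Counted from Cycle 3 Day 1, the Cycle 3 window ends at +2 and the Cycle 4 window opens at 28 - 2 = +26. Days -7 to -3 before Cycle 4 Day 1 are +21 to +25, inside that gap. The only other later rows concern treatment discontinuation and the 28-day follow-up, so a patient still on treatment has no row for these days.

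**Does another rule bring them in?**
- The closest-value rule chooses among values already within a window.
- The listing-only rule in SAP 4.1 concerns unscheduled tests; these tests are scheduled.
- The Cycle 0 study-day adjustment moves all days from Cycle 1 on by the same amount, so the gap stays.

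**Cycle 7 Day 1.** At nominal timing the count is again 5 of 8. PLD has ended by then, so the anchor depends on the branch of Table 4.
- *Combinations branch, PLD stopped.* The window is Cycle 6 Day 1 +26 to +30. If the actual Cycle 7 Day 1 is Cycle 6 Day 1 + 28 + s, the uncovered days number 5 - s for s from -2 to +2:

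| s (days) | -2 | -1 | 0 | +1 | +2 |
|---|---|---|---|---|---|
| Uncovered, of 8 | 7 | 6 | 5 | 4 | 3 |

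- *Monotherapy branch.* The protocol calls AZD7648 after Cycle 6 monotherapy. If this branch applies and AZD7648 is off on Cycle 6 Day 1 + 27, the lower limit is 2 days before the first AZD7648 intake after Cycle 6 Day 1 + 28. For a late Day 1 that again leaves days -7 to -3 uncovered, 5 of 8.

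A gap remains on either branch. The SAP does not settle which one applies, so the shifted counts in the table are conditional on the first.

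**The case against.** The strongest reply is that exclusion is inferred. No SAP sentence says that a protocol-compliant test outside Table 4 is dropped. SAP 3.2.1.12 works from scheduled assessment times, and the protocol defines that time for LVEF with its own 7-day allowance. A day -5 test could fairly be called the Cycle 4 Day 1 test. Table specifications are in a separate document that is not available here, so the programmed handling is unknown. This stands as a limit on certainty. It does not remove the conflict, because the SAP states a windowing rule by actual date and gives LVEF no exception to it.

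It is also true that ±2 days matches the protocol's general visit window. Table 4 is therefore not at odds with the schedule as a whole; one assessment-specific footnote was not carried over.

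The consequence is small. SAP 4.2.1 keeps LVEF results in listings, and SAP 3.1 uses all values for extreme-value and patient-level summaries. The example of n falling to 2 needs exactly three patients tested and one early test, and at n = 2 the minimum and maximum are both values. Development has been halted, outputs were cut, and an abbreviated CSR is planned. All of this stands, and it is why the point is minor.

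**Conclusion.** Wrong as written, minor. At nominal timing, 5 of the 8 protocol-compliant LVEF days before Cycle 4 Day 1 and Cycle 7 Day 1 have no analysis visit, and tests on those days do not reach one descriptive by-visit table. This rests on three assumptions: Table 4 governs LVEF, a value in no window is not assigned to a visit, and the patient is still on treatment.

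A reader might infer that five-eighths of the LVEF tests are lost, that falls in LVEF would go unreported, or that dose decisions are affected. The documents support none of these. Five of eight is a count of days, not of tests: booking dates and the numbers still on treatment at Cycles 4 and 7 are not given. The values remain in the listings. The LVEF decrease categories may or may not be counted by visit. The DLT period ends with Cycle 1, well before the first scheduled post-baseline LVEF test at Cycle 4.

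**What to change.** Add an LVEF row to SAP Table 4 for Cycle 4 Day 1 and Cycle 7 Day 1, and refer to it in SAP 3.2.1.12:
- **Window:** -7 to +2 days around the actual Day 1 dose of that cycle.
- **Anchor:** at Cycle 4 the PLD day, or the AZD7648 day if PLD has stopped; at Cycle 7 the AZD7648 day.
- **Fallback:** Day 1 of the previous cycle plus 28 days, only if no Day 1 dose of that cycle is given. This still assigns a visit to patients who stop before dosing.

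This row covers all 8 compliant days. At nominal timing it opens at +21 of the previous cycle, clear of that cycle's window, which ends at +2. Days +1 and +2 are kept because Table 4 counts them now, although footnote k asks for the test before dosing.

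The fallback should not be triggered merely because no test falls in the window. If PLD is delayed 10 days at Cycle 4, dosing is on Cycle 3 Day 1 + 38. Tests on +21 to +30 would then be 17 to 8 days before dosing, yet would be labelled Cycle 4 Day 1. With a 28-day delay (dosing on +56), the earliest would be 35 days before. Footnote k accepts none of these.

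The row has one side effect. On the Combinations branch at Cycle 7, if dosing is 6 or more days late, some days that Table 4 counts now fall out. They lie more than 7 days before the actual dose, so they are outside footnote k.

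The cost is one table row, one cross-reference and a change to the windowing program. No new data are needed. The basis for the LVEF decrease categories is a separate question and not part of this change.

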- Missing day and month – impute 1st January unless year is the same as first dose date then impute first dose date.
- Completely missing – impute with date of first dose of the study treatment, unless the end date suggests it could have started prior to this in which case impute with 1st January of the same year as the end date.
- Imputed start date should be no later than the end date.

For missing diagnostic dates, if day and/or month are missing use 01 and/or Jan. If year is missing, put the complete date to missing. Imputed dates will be used in the calculation of time since diagnosis.

If stop date is partial:

- Missing day - Impute the last day of the month unless both the month and the year are the same as the last dose date or the planned analyses data cut-off date, then impute the last dose date or the planned analyses data cut-off date.
- Missing day and month – impute 31st December unless the year is the same as the last dose date or the primary analysis data cut-off date then impute the last dose date or the primary analysis data cut-off date.
- Completely Missing – need to look at whether the AE/medication is still ongoing before imputing a date and also when it started in relation to study drug. If the ongoing flag is missing then assume that AE is still present / medication is still being taken (i.e. do not impute a date).

Flags will be retained in the database indicating where any programmatic imputation has been applied, and in such cases, any durations would not be calculated unless otherwise specified.

- If a patient is known to have died where only a partial death date is available then the date of death will be imputed as the latest of the last date known to be alive +1 from the database when the date is completely missing. Otherwise, the death date using the available information provided:
 - a. For Missing day only – using the 1st of the month
 - b. For Missing day and Month – using the 1st of January

Imputation for Laboratory Values Outside of Quantification Range

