3.2.2.1.2 Best objective response

Best objective response (BoR) is calculated based on the overall visit responses from each RECIST 1.1 assessment. (see Section 3.2.2.1.1). It is the best response a patient has had following first dose of study treatment on cycle 1, day 1; but prior to starting any subsequent cancer therapy or up to and including RECIST progression or the last evaluable assessment in the absence of RECIST progression. Categorisation of BoR will be based on RECIST 1.1 using the following response categories: CR, PR, SD, PD and NE.

The confirmation of CR or PR should be performed at the next RECIST assessment and must not be less than 4 weeks later. For determination of a best response of SD, the earliest of the dates contributing towards an overall visit assessment will be used. SD should be recorded at least 8 weeks minus 1 week (to allow for an early assessment within the assessment window), after first dose/administration of study medication at cycle 1. For CR/PR, the initial overall visit assessment which showed a response will use the latest of the dates contributing towards an overall visit assessment.

It will be determined programmatically based on RECIST using all site investigator data up until the first progression event. The denominator will be consistent with that used in the ORR analysis for the respective analysis set.

For patients whose progression event is death, BoR will be calculated based upon all evaluable RECIST assessments prior to death. For patients who die with no evaluable RECIST assessments post-baseline, if the death occurs ≤ 17 weeks (i.e., 16 weeks + 1 week to allow for a late assessment within the assessment window) after first dose/administration of study medication at cycle 1, day 1, then BoR will be assigned to the progression (PD) category. For patients who die with no evaluable RECIST assessments, if the death occurs > 17 weeks after start of treatment at cycle 1 then BoR will be assigned to the NE category.

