3.2.2.1.6 Progression Free Survival

PFS is defined as the time from first dose of Cycle 1 until the date of objective disease progression or death (by any cause in the absence of progression) regardless of whether the patient withdraws from study therapy or receives another anti-cancer therapy prior to progression (i.e. date of PFS event or censoring – date of first dose + 1). Patients who have not progressed or died at the time of analysis will be censored at the time of the latest date of assessment from their last evaluable RECIST assessment. However, if the patient progresses or dies after two or more missed visits, the patient will be censored at the time of the latest evaluable RECIST 1.1 assessment prior to the two missed visits.

If the patient has no evaluable post-baseline visits or does not have baseline data they will be censored at Day 1 unless they die within 2 visits of baseline (16 weeks plus 1 week allowing for a late assessment within the visit window).

The PFS time will always be derived based on scan/assessment dates, not visit dates.

RECIST assessments/scans contributing towards a particular visit may be performed on different dates.

The following rules will be applied:

- For investigational assessments, the date of progression will be determined based on the earliest of the dates of the component that triggered the progression
- When censoring a patient for PFS the patient will be censored at the latest of the dates contributing to a particular overall visit assessment

Note: for TLs only the latest scan date is recorded out of all scans performed at that assessment for the TLs and similarly for NTLs only the latest scan date is recorded out of all scans performed at that assessment for the NTLs.

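### SAP 3.1 applies the last-known-alive + 1 floor only to wholly missing death dates, so a partly known death can be dated before the patient was last known alive

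*SAP*

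**What the plan says.** The rule is at the end of the partial-date text in SAP 3.1 (General principles). For a patient known to have died, the death date is "imputed as the latest of the last date known to be alive +1 from the database when the date is completely missing". The text continues "Otherwise, the death date using the available information provided" and gives two branches: "For Missing day only – using the 1st of the month" and "For Missing day and Month – using the 1st of January". Neither branch refers to the last date known alive. The phrase about taking the latest is followed by one date only, so it has nothing to compare.

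Other dates in the section are constrained. Partial start dates are tied to first dose, with the check "Imputed start date should be no later than the end date". Partial stop dates are tied to last dose or data cut-off. No ordering check is stated for death, in this section or elsewhere in the two documents.

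Just before the death rule, the SAP says that imputed dates are flagged and that "in such cases, any durations would not be calculated unless otherwise specified".

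The death date is used in four derivations:
- **PFS (SAP 3.2.2.1.6):** "PFS is defined as the time from first dose of Cycle 1 until the date of objective disease progression or death".
- **Duration of response (SAP 3.2.2.1.4):** it ends on the PFS event or censoring date.
- **Best objective response (SAP 3.2.2.1.2):** for patients who die with no evaluable post-baseline RECIST assessment, death at or before 17 weeks gives PD, and "if the death occurs > 17 weeks after start of treatment at cycle 1 then BoR will be assigned to the NE category".
- **Total treatment duration (SAP 3.2.1.1):** date of death is one of the terms in a minimum.

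**The concern.** A patient seen alive on the 20th of a month who dies later that month, day unknown, is given a death on the 1st. The data set then holds a visit or a scan after death. If only the year is known, the imputed death can fall before treatment began.

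Partial death dates are plausible here. Protocol 7.1.3 allows modified follow-up through a relative, a treating physician or medical records, and Protocol 7.3 takes vital status from public sources. Cohorts hold 1 to 6 patients in the Core Module (Protocol 9.2) and 3 to 6 in Combination Module 1 (Protocol 16.2), so one misdated death can show in a cohort's summary.

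**Working it through.** The plan gives no figure to reproduce. The check codes the rule as written and compares it with a rule that has the floor in every branch.

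**Rules**
- Literal: wholly missing = last alive + 1; day missing = 1st of the month; day and month missing = 1 January.
- Floored: the later of (last alive + 1) and the literal partial date.
- PFS = event date − Cycle 1 first dose + 1 (SAP 3.2.2.1.6).

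**Example** (assumed dates: Cycle 1 Day 1 on 1 March 2021, last known alive 20 June 2021, no progression)

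| Death recorded as | Literal date | Days from last alive | PFS, literal | Floored date | PFS, floored |
|---|---|---|---|---|---|
| June 2021 | 1 June | −19 | 92 + 1 = 93 | 21 June | 112 + 1 = 113 |
| 2021 | 1 January | −170 | −59 + 1 = −58 | 21 June | 113 |
| July 2021 | 1 July | +11 | 122 + 1 = 123 | 1 July | 123 |
| Wholly missing | 21 June | +1 | 113 | 21 June | 113 |

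The error arises when the last-alive date is in the same month (or year) as the recorded death but after its first day. The largest backdating is 31 − 1 = 30 days with the day missing and 365 − 1 = 364 days with day and month missing (365 in a leap year).

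**How often, day missing.** Assume death is equally likely on each day of a 365-day year and last contact was g days earlier. The imputed date precedes last contact when day of month − g > 1. Counts are over seven 31-day months, four 30-day months and February:
- g = 7: 7×23 + 4×22 + 20 = 269; 269/365 = 74%
- g = 14: 7×16 + 4×15 + 13 = 185; 51%
- g = 21: 7×9 + 4×8 + 6 = 101; 28%
- g = 28: 7×2 + 4×1 + 0 = 18; 5%
- g = 31 or more: 0%

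**Best objective response and censoring.** Keep first dose at 1 March 2021 and assume no evaluable post-baseline scan, last known alive 29 June, death recorded as June 2021. The floored date is 30 June, 121 days after first dose and beyond 17 × 7 = 119 days: best response NE, and PFS censored at Day 1 under SAP 3.2.2.1.6. The literal date is 1 June, 92 days after first dose: best response PD, and a PFS event at day 93. Similarly, a death after two missed visits, which that section censors at the earlier scan, can be moved back far enough to count as an event.

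**Treatment duration.** If the imputed death precedes the last dose, the minimum in SAP 3.2.1.1 selects the death date and the later dosing days are lost.

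**The case against.** The strongest reply is that durations are not calculated from imputed dates, so PFS and duration of response cannot be distorted. The sentence is there, but it follows the adverse event and medication stop-date rules and precedes the death rule, and its reach to death is not stated. If it does apply, those patients have no PFS time and no stated handling. It would also leave the death date itself, the 17-week best-response rule and the treatment-duration minimum uncorrected. This reply limits the certainty of the PFS effect; it does not remove the defect.

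A second reply is that the slip is obvious and a programmer would restore the comparison. That is likely the intent, but the SAP is the specification and two programmers could code it differently.

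The third reply is that little is at stake, and much of this stands. Protocol 9.1 plans no hypotheses. SAP 1.1 limits efficacy output, and the version history records removal of the overall survival section. Medians and Kaplan-Meier output for duration of response, and PFS medians and quartiles, depend on sufficient data. Date of death is collected directly (Protocol 8.3.4 and 8.3.11). Death counts for PFS only if no progression came first. Scheduled contact is often sparse: Day 1 of each 28-day cycle from Cycle 3, one 28-day follow-up visit, then scans every 8 weeks until progression (Protocol Table 1 and 8.1.1). At such gaps the missing-day problem nearly or wholly disappears, although the missing-month branch stays exposed.

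Two stronger readings are not supported:
- A reader might take the average distance between true and imputed death, 14.7 days with the day missing and 182 with day and month missing, as the size of the error. Those averages describe the first-of-period convention, which the fix keeps. With the floor added, the missing-day average is still 5.3, 10.0 and 13.1 days at gaps of 7, 14 and 21 days, so the missing floor accounts for 9.4, 4.7 and 1.6 days.
- A reader might infer that best response is at risk generally. The 17-week rule covers only patients with no evaluable post-baseline assessment, and a switch between NE and PD leaves ORR unchanged.

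**Conclusion.** The defect is real: as written, the rule can return a death before the patient was last known alive and, with only the year known, before first dose. Backdating is at most 30 days with the day missing and about 364 days with day and month missing. The 74% to 0% range rests on assumed contact gaps and uniform death days. The documents do not say how many deaths have partial dates, so the effect on any summary cannot be quantified; few patients are probably involved. The cause looks like a lost term in one sentence rather than a chosen method. It should be corrected because the result is impossible on its face and the death date feeds several derivations. The documents do not support a claim of material bias in the study's efficacy results.

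**What to change.** Replace the death-date rule in SAP 3.1 with: *The death date is imputed as the later of (a) last date known alive + 1 and (b) the 1st of the month (day missing) or 1 January (day and month missing); if completely missing, use (a).*

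Add that PFS and duration of response are calculated from imputed death dates, despite the general statement about durations where dates are imputed.

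The cost is two sentences in the SAP and a one-line change in the derivation program, with no new data. The first-of-period convention stays, so a death can still be dated early and can still cross the 17-week line, but not before a date on which the patient was known to be alive.
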